Summary statistics will be tabulated by treatment arm for the baseline, week 4, and week 8 outcome measures of VABS, NPI, and protocol adherence based on behavior journals. The change from baseline to week 4 and follow-up will be calculated for each patient. Descriptive statistics will be examined to see whether levels of each assessment at baseline are normally distributed. If they are, then the mean changes will be compared in each treatment group with the standard of care group by analysis of variance (ANOVA). If they are not normal, then consideration will be given to data transformation.

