Once eligibility is confirmed, the research assistant will email a REDCap link to the caregiver for the Zarit Caregiver Burden and the Adult Sensory Profile, Actigraph and charger, and a copy of consent forms to the participant's caregiver. The PI will complete the COPM on visit 1, and provide caregiver and participant with Actigraph wear and care instructions. The VABS will be emailed to the caregiver via a confidential link through Pearson Publishing.

Subjects will be randomized to treatment arms by the statistical team. Participants will be randomized into one of the three groups: control, standard environmental design protocol, individualized environmental design protocol. Recruitment will be ongoing until all groups have 10 participants. In the event of drop out or early termination (causes will be recorded), researchers will recruit for replacement participants so that the study is completed with 30 entire study duration cases.

Visit 2 will consist of baseline assessment. A research assistant or the PI will complete the MOCA, with the participant with dementia. The caregiver will complete the NPI. Following Visit 2, an occupational therapist will be provided results of the COPM and ASP for participants of the individualized treatment arm. A sensory protocol will be developed based on assessment results following predetermined guidelines. All intervention materials for all study participants will be mailed to caregivers within 4 days of Visit 2. Upon receipt of intervention supplies, caregivers will contact the PI or occupational therapist for study initiation. Visit 3 will provide caregiver training for intervention use and initiation of Actigraph use. Adverse events since Visit 2 will be recorded. Visit 3 marks day 1 of intervention implementation. Participants will mail Actigraph back to UKADC in provided pre-paid envelop following week one of intervention.

Visits 4-8 will be scheduled at the end of each week following Visit 3. The PI, occupational therapist, or research assistant will record concurrent medication, and adverse events. With the caregiver, the interviewer will review behaviors observed by the caregiver, the behavior journal, compliance and acceptance of the intervention by the caregiver and the person with dementia. Actigraphs will be mailed from UKADC to participants, and patient will be asked to wear actigraph for last week of intervention window.

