Visit 9 will conclude the intervention window at the end of week 4. The PI, occupational therapist, research assistant will record adverse events, concurrent medication, Actigraph, and weekly behavior journals/compliance. The research assistant will conduct the NPI, COPM, VABS with the caregiver and the MOCA with the person with dementia. A member of the SBCoA medical team will conduct a physical and neurological exam. Due to the length of assessments within Visit 7, this session may be split and completed in more than one Zoom conference. The Zarit Caregiver Burden Scale will be emailed or mailed to the caregiver with prepaid envelop for return.

A four-week follow up will be conducted at Visit 10 whereby the research assistant will conduct the NPI, COPM, VABS with the caregiver, and the MOCA with the person with dementia. A member of the SBCoA medical team will conduct a physical and neurological exam. The Zarit Caregiver Burden Scale will be emailed or mailed to the caregiver with prepaid envelop for return.

Schedule of events can be found in attached detailed protocol.

A list of potential items sent in sensory kit is attached here.

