#### Vineland Adaptive Behavior Scale (VABS)

The VABS will be used to assess behavior at baseline, week 4, week 8. The VABS is a standardized, norm-referenced assessment of adaptive behavior for individuals from birth to age of 90 years. Domains of communication, daily living skills, socialization, motor skills, and maladaptive behavior are examined. The assessment is designed for a variety of developmental, intellectual, and cognitive disabilities, including autism spectrum disorder, ADHD, traumatic brain injury, and Alzheimer's disease and related disorders. This assessment has an option specific for telehealth, remote administration. For this study, change in the Adaptive Behavior Composite (ABC) score, as well as domain specific scores of communication, daily living skills, socialization, and motor skills will be used in analysis.

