## Attachments

Attach Type	File Name
DataCollection	CDR.pdf
DataCollection	Behavior journal.pdf
DataCollection	COPM.pdf
DataCollection	Form M Sensory.pdf
DataCollection	MoCA-Test-English_7_1.pdf
DataCollection	ZBI-22_AU1.0_eng-USori_ReviewCopy-1.pdf
DataCollection	Vineland-3 Interview (002).pdf
DataCollection	hpiq-questionnaire.pdf
DataCollection	SituationalAssessmentOfActivit.pdf

**Resources:** Describe what resources/facilities are available to perform the research (i.e., staff, space, equipment). Such resources may include a) staffing and personnel, in terms of availability, number, expertise, and experience; b) psychological, social, or medical services, including counseling or social support services that may be required because of research participation; c) psychological, social, or medical monitoring, ancillary care, equipment needed to protect subjects; d) resources for subject communication, such as language translation services, and e) computer or other technological resources, mobile or otherwise, required or created during the conduct of the research. Please note: Some mobile apps may be considered mobile medical devices under FDA regulations (see [FDA Guidance](#)). Proximity or availability of other resources should also be taken into consideration, for example, the proximity of an emergency facility for care of subject injury, or availability of psychological support after participation.

Research activities conducted at performance sites that are not owned or operated by the University of Kentucky, at sites that are geographically separate from UK, or at sites that do not fall under the UK IRB's authority, are subject to special procedures for coordination of research review. Additional information is required (see [IRB Application Instructions - Off-Site Research](#) web page); supportive documentation can be attached in the E-IRB "Additional Information" section. Provide a written description of the role of the non-UK site(s) or non-UK personnel who will be participating in your research. The other site may need to complete its own IRB review, or a cooperative review arrangement may need to be established. Contact the Office of Research Integrity at [contact] if you have questions about the participation of non-UK sites/personnel.

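### The VABS is emailed to the caregiver at baseline but conducted by a research assistant at weeks 4 and 8, so within-arm change mixes mode of administration with behaviour

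*Combined protocol and SAP*

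**What the plan says.** All references are to the combined protocol and SAP.

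- **Baseline VABS** (Research Description, Research Procedures, after eligibility is confirmed): "The VABS will be emailed to the caregiver via a confidential link through Pearson Publishing". No interviewer is mentioned.
- **Week 4** (Research Procedures, Visit 9): "The research assistant will conduct the NPI, COPM, VABS with the caregiver and the MOCA with the person with dementia".
- **Week 8** (Research Procedures, Visit 10): "A four-week follow up will be conducted at Visit 10 whereby the research assistant will conduct the NPI, COPM, VABS with the caregiver".
- **Instrument text** (Data Collection, VABS): "The VABS will be used to assess behavior at baseline, week 4, week 8". It mentions that a telehealth option exists but fixes no mode for any visit.
- **Form supplied** (Data Collection, Attachments): "Vineland-3 Interview (002).pdf" is the only VABS file listed.
- **Use in the analysis** (Study Design, Data Analysis): "The change from baseline to week 4 and follow-up will be calculated for each patient". Mean changes are then compared with standard of care by ANOVA. The closing Statistical Analysis section instead uses ANCOVA of the end-of-intervention value adjusted for baseline.

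**The concern.** A form that a caregiver fills in alone and an interview in which a research assistant can probe and clarify need not give the same score for the same person. Here the switch falls exactly between the baseline value and both later values. Within one arm, nothing in the data can separate the effect of the switch from a change in behaviour.

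Two things are at stake. First, the VABS changes tabulated by arm could be read as improvement or deterioration when part or all of the movement comes from the method. This matters in a pilot with 10 per arm whose first objective names behaviour change and whose behaviour results are meant to be descriptive. Second, a baseline taken by another method may predict the outcome less well, and baseline adjustment then gains less precision.

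**Working it through.** **Step 1. Set the passages side by side.**

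| Measure | Baseline | Week 4 (Visit 9) | Week 8 (Visit 10) |
|---|---|---|---|
| VABS | Link emailed to caregiver | Research assistant, with caregiver | Research assistant, with caregiver |
| NPI | Procedures: caregiver completes it. Instrument text: given with the caregiver | Research assistant, with caregiver | Research assistant, with caregiver |
| COPM | Caregiver interview by the PI; caregiver's ratings | Caregiver interview by research assistant; caregiver's ratings | Same as week 4 |

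Only the VABS row shows a change of mode on plain reading. The wording does not look accidental. The Visit 9 and Visit 10 paragraphs separately have the caregiver burden scale emailed or mailed, so the text distinguishes forms that are sent out from assessments that are conducted.

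**Step 2. Inputs for size.** The documents give 10 per arm. They give no VABS standard deviation, baseline-outcome correlation or mode effect, and there is no stated power figure to reproduce. The following are therefore assumptions: a mode shift m of 0.2 to 0.5 SD, the same in every arm; a baseline-outcome correlation r of 0.4 to 0.8; and equal SDs at both times.

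**Step 3. Within an arm.** With no true effect, expected mean change = m. SD of change = √(2(1 − r)), and SE of the mean change = that SD / √10.

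- r = 0.8: √0.4 = 0.632; SE = 0.200 SD
- r = 0.6: √0.8 = 0.894; SE = 0.283 SD
- r = 0.4: √1.2 = 1.095; SE = 0.346 SD

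A shift of 0.2 SD is thus 0.6 to 1.0 standard errors, and a shift of 0.5 SD is 1.4 to 2.5. In a simulation (20,000 runs, 10 per arm, no true effect), a nominal 5% paired test within one arm rejected in 8% to 15% of runs for m = 0.2 and in 25% to 61% for m = 0.5. The plan does not specify such a test. The figures only show how easily the tabulated change could mislead.

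**Step 4. Between arms.** If mean change is (effect + m) in a treated arm and m in control, the difference is the effect alone. In ANCOVA a common m goes into the intercept. In the simulation, the between-arm difference stayed within 0.01 SD of zero by either method, and ANCOVA type I error stayed at about 5%.

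**Step 5. Precision.** ANCOVA residual variance is 1 − r² of the outcome variance. If mixing modes lowered r from 0.8 to 0.6:

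- Residual variance goes from 0.36 to 0.64: ratio 0.64 / 0.36 = 1.78. The SE ratio is 0.80 / 0.60 = 1.33.
- For ANOVA on changes, variance 2(1 − r) goes from 0.4 to 0.8, and the SE ratio is √2 = 1.41.
- With ANCOVA at 10 per arm, power for a 0.8 SD difference between two arms (two-sided 5%, normal approximation) falls from about 85% to 61%.

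**The case against.** The strongest reply is that the trial is randomised and its planned tests compare arms. A shift common to all arms cancels there, no within-arm pre-post test is specified, and the VABS is a secondary, exploratory measure. All of this stands, and it confines the point to the interpretation of within-arm change and to precision.

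It can also be said that the VABS mode is less certain than it looks. An interview form as the only attachment would fit interviews at every visit, and the schedule of events sits in a detailed protocol that is not among the documents. That file may settle the matter. The procedures text still describes two modes, and the instrument text does not resolve it.

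A reader might infer four stronger things that the documents do not support:

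- **That the NPI also changes mode.** At Visit 2 the text says "The caregiver will complete the NPI", but the NPI instrument text describes the same caregiver administration at all three times. The procedures also use the verb complete for assessments that staff carry out, as in "The PI will complete the COPM on visit 1". This is wording to reconcile, not an established mode change.
- **That the COPM changes rater.** Its instrument text describes a semi-structured caregiver interview at every time point and analyses the caregiver's own ratings. Only the interviewer differs: the PI, then the research assistant.
- **That the treatment comparison is biased.** This would need a mode effect that differs by arm, and nothing in the documents shows one.
- **That interviewers who know the arm distort the follow-up scores.** The plan says single-blind without saying who is blinded. Whatever the answer, it is a separate matter that using one mode would not resolve.

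**Conclusion.** The point holds for the VABS. As written, its mode of administration changes between baseline and both later assessments, so within-arm VABS change cannot be attributed to behaviour. The size of the artefact is unknown. Under the assumed range it would be 0.2 to 0.5 SD of spurious mean change in each arm, control included. The between-arm estimate is not biased by a shift that is additive and common to the arms. The possible loss there is precision, for example 33% larger ANCOVA standard errors if the correlation falls from 0.8 to 0.6, and neither correlation comes from the documents. This is a modest, cheaply corrected weakness in a secondary measure and does not undermine the randomised comparison.

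**What to change.** Amend Research Procedures and the VABS instrument text to state one VABS mode for baseline, week 4 and week 8. There are two ways to do this:

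- **Emailed form each time.** This adds no interviews and removes the two now planned per dyad. The caregiver form behind the link should be added to the listed attachments.
- **Research-assistant interview each time.** This costs one extra baseline interview per dyad, or 30 for the planned 30 dyads. It needs no new instrument or staff role.

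The file is marked closed and the Statistical Analysis section is written in the past tense, so some or all dyads may already have been assessed. For those, report the mode used at each time point and do not interpret within-arm VABS change as behaviour change. Between-arm results can be kept, with a note that baseline and outcome were collected differently.

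Separately, reconcile the NPI wording between Research Procedures (Visits 2, 9 and 10) and the NPI instrument text. This point calls for no change to the COPM.

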#### Attachments

Attach Type	File Name
ResearchProcedures	Sensation Kit.pdf

**Data Collection:** List the data or attach a list of the data to be collected about or from each subject (e.g. interview script, survey tool, data collection form for existing data).

If the research includes survey or interview procedures, the questionnaire, interview questions or assessment scales should be included in the application (use attachment button below).

The data collection instrument(s) can be submitted with your application in draft form with the understanding that the submitted to the IRB for approval prior to use (submit final version to the IRB for review as a modification request if initial IRB approval was issued while the data collection instrument was in draft form).

Note: The IRB approval process does not include a statistical review. Investigators are strongly encouraged to develop data management and analysis plans in consult with a statistician.

#### Neuropsychiatric Inventory

The NPI-Q will be administered with the caregiver at baseline, week 4, and week 8. The NPI-Q is a commonly used behavior assessment tool for persons with cognitive impairment.[63] This tool was selected in order to best represent behaviors characteristic of cognitive impairment. The assessment includes 12 behavioral and psychiatric domains including delusions, hallucinations, irritability, anxiety, agitation, depressions, dysphoria, apathy, disinhibition, aberrant motor behavior, appetite/eating changes, and night-time behaviors. The care provider rates these behaviors based on severity of the impact on the patient on a scale of 1 (mild), 2 (moderate), or 3 (severe). The care provider also rates distress to themselves caused by each behavior on a scale from 0 (not distressing at all) to 5 (extreme or very distressing). Both behavior severity and caregiver distress will be used in analysis.

#### Vineland Adaptive Behavior Scale (VABS)

The VABS will be used to assess behavior at baseline, week 4, week 8. The VABS is a standardized, norm-referenced assessment of adaptive behavior for individuals from birth to age of 90 years. Domains of communication, daily living skills, socialization, motor skills, and maladaptive behavior are examined. The assessment is designed for a variety of developmental, intellectual, and cognitive disabilities, including autism spectrum disorder, ADHD, traumatic brain injury, and Alzheimer's disease and related disorders. This assessment has an option specific for telehealth, remote administration. For this study, change in the Adaptive Behavior Composite (ABC) score, as well as domain specific scores of communication, daily living skills, socialization, and motor skills will be used in analysis.

#### Adult Sensory Profile (ASP)

In order to maximize time consideration, the ASP will be mailed to caregivers following screening with a prepaid return envelope. The ASP is a validated instrument and will yield norm referenced (for age) data regarding sensory processing abilities and will be used in development of individualized protocols, as is typical in occupational therapy clinical practice.[35, 64, 65] The ASP is a 60-item survey and is completed by the participant or their care partner. For this study, care partners will complete the survey. Each item describes a behavior attributed to sensory processing. The behaviors belong to one of four sensory processing patterns (15 items each): low registration, sensation seeking, sensory sensitivity, and sensation avoiding. Participants rate the frequency with which they engage in each behavior or they observe it in the participant, in the case of caregivers responding. The ratings for all items are summed within each sensory processing pattern to obtain summary scores. The summary score of each category is compared to normative data and classified as being 'much less', 'less', 'similar', 'more than' or 'much more' than most people in their age range.

#### Behavioral Journal

Behavior journals will be kept by caregivers daily during the 4-week intervention. Behavior journals will be used to measure adherence to the treatment protocol using a daily tracking log, prompt care partner reflection of each week's intervention use, and monitor behavioral changes throughout the intervention. Journals will be reviewed weekly with study personnel and returned to investigator at intervention completion on week 4 visit. Analysis will include quantitative

#### Actigraph Wrist Wearable

The Actigraph wGT3X-BT will be used to collect behavioral and physiological data of sleep, movement, and physical activity. The device will be worn during baseline (1 week), first week of treatment (1 week), and last week of treatment (1 week). The device will be mailed back to UKADC during treatment window for charging and data collection, and mailed to patient prior to last week of treatment. The device will be returned to UKADC via prepaid postage following last week of intervention. The data will be collected off of the device following completion of the 4-week intervention window and stored in ActiLife 6, a private and secure platform for data acquisition from Actigraph. All data will be deidentified and stored in REDCap.

#### Montreal Cognitive Assessment (MoCA)

The MoCA is a rapid screening instrument for mild cognitive dysfunction. The MoCA assesses different cognitive domains: attention and concentration, memory, language, conceptual thinking, calculations, and orientation. Time to administer the MoCA is approximately 5-10 minutes. The total possible score is 30 points; a score of 18 or above is considered normal.

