Current research lacks sensory-based assessment, individualization of intervention, use of protocols, and is plagued with methodological errors creating mixed results. Individual sensory programs, also known as sensory diets, have been shown effective for decreasing agitation in various neurological disorders, but have not been well-established with individual assessment, development and implementation in dementia care. Once established, environmental design protocols for ADRD care will likely decrease burdensome BPSD, decrease need for institutional care, and possibly delay mortality while preserving quality of

life.43 The need for well-designed non-pharmacological interventions for BPSD is significant.44 Application of the described here is driven by clinical observations across the lifespan and can have immediate translation into treatment options for BPSD.

**Objectives:** List your research objectives. You may reference grant application/sponsor's relevant protocol pages and attach as an appendix in the E-IRB "Additional Information" section, however, a summary paragraph must be provided in the text box below.

1. To assess feasibility of environmental design protocols for intervention adherence and behavior change in subjects with moderate to severe dementia.
2. To evaluate sensory processing patterns and preferences of subjects with moderate to severe dementia.
3. To assess behavioral impact of environmental design intervention on functional activity engagement and cognition.

**Study Design:** Describe the study design (e.g., single/double blind, parallel, crossover, etc.). Indicate whether or not the subjects will receive placebo medication at some point in the research procedures. Also, indicate whether or not the subjects will be randomized in this study. You may reference sponsor's protocol pages and attach as an appendix in the E-IRB "Additional Information" section, however, a summary paragraph must be provided in the text box below. (Including the study design table from a sponsor's protocol is helpful to IRB members.)

**Community-Based Participatory Research:** If you are conducting [community-based participatory research \(CBPR\)](#), describe strategies for involvement of community members in the design and implementation of the study, and dissemination of results from the study.

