**Research Repositories:** If the purpose of this submission is to establish a Research Repository (bank, registry) indicate whether the material you plan to collect would or would not be available from a commercial supplier, clinical lab, or established IRB approved research repository. Provide scientific justification for establishment of an additional repository collecting duplicate material. Describe the repository design and operating procedures. For relevant information to include, see the [UK Research Biospecimen Bank Guidance](#) or the [UK Research Registry Guidance](#).

This study will use a single-blind, placebo controlled, three-arm, parallel-design. Thirty subjects with moderate to severe Alzheimer's disease as primary dementia type (Clinical Dementia Rating Scale score of 2-3) will be randomly assigned to one of three arms: standard care; standard protocol (pre-determined set of environmental design modifications); or personalized protocol (environmental design modification developed with subject based on sensory preference and behavioral needs). Intervention will last 4 weeks. Weekly monitoring for protocol adherence and adverse events will occur throughout study. An follow-up 4 weeks post-intervention will occur. The entire project will be conducted over 10 weeks of participant engagement.

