- Caregiver burden will be measured using the Zarit Caregiver Burden Scale.

Secondary measures:

- Behavior will be assessed using the Vineland Adaptive Behavior Scales (VABS) and the Neuropsychiatric Inventory (NPI) at baseline and post-intervention, and behavior tracking throughout intervention.
- Cognitive measures will include the MOCA and CDR at baseline, post-intervention and follow up
- Heart rate tracking and sleep will be measured using wearable activity tracker (Actigraph) at all times except while charging device.

Sensory processing patterns and functional activity engagement will be assessed for all participants with dementia and used for individualization arm of intervention.

- Sensory processing will be measured using the Adult Sensory Profile (ASP) for all subjects at baseline.
- Functional activity engagement will be measured using the Canadian Occupational Performance Measure (COPM) at baseline and post-intervention.

**Control Group:** Standard of care for behavioral management and 2-page educational pamphlet describing safety for home environments. At the conclusion of the study, following the four-week follow up visit, participants will be offered a standardized sensory kit (as described below) to use at their discretion.

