#### Inclusion Criteria:

Participants must meet all of the following inclusion criteria in order to participate in the study:

1. Men or women aged 21-90, inclusive.
2. Living at home in the community with one primary caregiver.
3. Diagnosis of Alzheimer's disease as primary dementia type of moderate to severe stages (confirmed by Clinical Dementia Rating Scale score of 1.5+)
4. Stable medical condition for one month prior to screening visit
5. Stable medications for 4 weeks prior to screening visit
6. If on psychotropic medication, they are at a point where dosage and treatment are stabilized for the duration of the study
7. Physically acceptable for this study as confirmed by medical history, physical exam, neurological exam and clinical tests completed by MD/APRN/PA
8. Functional sensory abilities with or without aids (hearing, vision, smell, touch, taste)
9. Caregiver report of challenges related to behaviors within 4 weeks of study enrollment
10. Caregiver willing to participant throughout duration of study
11. Caregiver access to and ability to use video technology (Zoom video call)
12. UKADC visit with medical provider within 24 months of study recruitment
13. Not actively participating in physical/occupational therapy for four weeks prior to or throughout duration of study

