For additional details, see topic "Recruitment of Subjects/Advertising" on ORI's [IRB Survival Handbook web page](#) and the [PI Guide to Identification and Recruitment of Human Subjects for Research](#).

The University of Kentucky SBCoA will assist in participant identification based on the participant database for the University of Kentucky Alzheimer's Center Longitudinal Cohort. Participants who have a Clinical Dementia Rating Score of 1.5 or above and reside in the community will be targeted for recruitment. Additional referrals will also be requested from SBCoA medical team staff. Of individuals identified, flyers will be mailed or emailed to the LAR on file with SBCoA and primary caregivers will be contacted via flyer and phone call from study personnel staffed at SBCoA. In addition, all patients with memory impairment of the Kentucky Neuroscience Institute (KNI) who are eligible for this study may be recruited for participation for this study. Recruitment from KNI will occur prior to informed consent including a review of medical records to identify additional subjects that are not in the recruitment database. This PHI information will be collected via AEHR UKHC (or EPIC). A waiver of informed consent is requested with this protocol. Information that will be collected prior to informed consent will include identifiable private health information including: Name, email address, phone number, DOB, address, medical history, diagnoses, medications, tests completed at SBCoA or KNI. Upon identification of eligible participants, the KNI medical team will determine patient interest to be contacted by study personnel and notify [name] (PI) to follow up with contact to potential participants and/or the study flyer will be mailed or emailed to eligible patients with request to contact study personnel if interested in study participation.

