#### CDR (Clinical Dementia Rating)

The CDR will be administered to the participant and informant, at screening, week 24 and week 48 and will be administered by a certified tester. During the CDR is a structured interview protocol that assesses a patient's cognitive and functional performance in six areas: memory, orientation, judgment & problem solving, community affairs, home & hobbies, and personal care. Scores in each of these are combined to obtain a composite score ranging from 0 through 3. The CDR can discern very mild impairments, based on informant interview and short task-based participant responses.

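### In moderate to severe dementia the MoCA risks a floor and the CDR composite cannot record worsening at 3; the ANCOVA allows for neither, so a null cognition result could be misread as no effect

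*Combined protocol and SAP*

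**What the plan says.** All places are in the combined protocol and SAP.

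- **Objective.** Research Description, Objectives, item 3: "To assess behavioral impact of environmental design intervention on functional activity engagement and cognition".
- **Measures.** Secondary measures: "Cognitive measures will include the MOCA and CDR at baseline, post-intervention and follow up". No other cognitive measure is listed.
- **MoCA.** Data Collection: "The MoCA is a rapid screening instrument for mild cognitive dysfunction", and "The total possible score is 30 points; a score of 18 or above is considered normal".
- **CDR.** Data Collection names six areas and adds: "Scores in each of these are combined to obtain a composite score ranging from 0 through 3".
- **Population.** Study Design gives a "Clinical Dementia Rating Scale score of 2-3". Inclusion criterion 3 has moderate to severe disease "confirmed by Clinical Dementia Rating Scale score of 1.5" or more, and the recruitment text agrees: "Participants who have a Clinical Dementia Rating Score of 1.5 or above and reside in the community will be targeted for recruitment". The Informed Consent Process section expects severe impairment with possible communication deficits, and plans for participants who cannot answer verbally.
- **CDR timing.** Secondary measures has it at baseline, post-intervention and follow-up. The CDR paragraph has it at screening, week 24 and week 48. Research Procedures does not list it at Visit 9 or Visit 10. Study Design gives 10 weeks of participant engagement.
- **Analysis.** The Statistical Analysis section applies baseline-adjusted ANCOVA to all secondary and exploratory endpoints. Its sensitivity analyses cover imputation, extra covariates and the four-week follow-up. None deals with scores at a limit.

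**The concern.** By the protocol's own account, the MoCA is designed to detect mild dysfunction, and it is being used as an outcome in people well beyond that stage. Some participants may score at or near zero. A person at zero cannot show decline, and may improve somewhat without leaving zero.

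The CDR composite reduces six area scores to one number spanning three points, and it cannot rise above 3. That limit blocks worsening, not improvement. Worsening still matters here: the Potential Risks section lists greater confusion and poorer orientation among the signs of sensory overload from the intervention. Cognitive decline is thus a harm the protocol itself foresees.

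An ANCOVA of means treats tied scores at a limit as ordinary values and pulls the estimated arm difference towards zero. The Data Analysis text says only that transformation will be considered if baseline scores are not normal, and no transformation separates people tied at one value. What is at stake is how a null cognition result is read, for benefit and for harm.

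**Working it through.** **There is no plan figure to reproduce.** The sample size is 3 arms × 10 = 30. No alpha, power, effect size or SD is given, and no expected MoCA mean, SD or share at zero.

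**CDR: room to move on a 0–3 composite**

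| Entry score | Room to worsen | Room to improve |
|---|---|---|
| 1.5 | 3 − 1.5 = 1.5 | 1.5 |
| 2 | 3 − 2 = 1 | 2 |
| 3 | 3 − 3 = 0 | 3 |

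Only an entry score of 3 is at the limit, and only for worsening. This is so under either entry criterion.

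**MoCA: what a floor would do.** All inputs here are assumptions: a normal latent score with SD 5 at both times, a true change of 3 points, and baseline-to-end correlation 0.8 (used for power only). Scores are rounded and limited to 0–30. The latent mean m is varied because the documents do not fix it.

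- Share scored zero at baseline: Φ((0.5 − m)/5). For m = 5 this is Φ(−0.9) = 18%. For m = 0 it is Φ(0.1) = 54%.
- Mean score with a floor at zero, ignoring rounding: E(m) = m·Φ(m/5) + 5·φ(m/5).
- For m = 5 and a true +3: E(8) − E(5) = 8.12 − 5.42 = 2.70, and 2.70/3 = 90% kept.
- For m = 0 and a true +3: E(3) − E(0) = 3.84 − 1.99 = 1.85, and 1.85/3 = 62% kept.

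Simulation with rounding gives the same means. It also gives the power of a two-arm ANCOVA with 10 per arm (two-sided 5%, true +3):

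| Latent mean | At zero at baseline | True +3 recorded as | Kept | True −3 recorded as | Kept | Power |
|---|---|---|---|---|---|---|
| 12 | 1% | 2.99 | 100% | −2.94 | 98% | 0.53 |
| 8 | 7% | 2.91 | 97% | −2.70 | 90% | 0.53 |
| 5 | 18% | 2.70 | 90% | −2.27 | 76% | 0.50 |
| 2 | 38% | 2.27 | 76% | −1.62 | 54% | 0.43 |
| 0 | 54% | 1.85 | 62% | −1.15 | 38% | 0.35 |
| −3 | 76% | 1.15 | 38% | −0.56 | 19% | 0.21 |

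With no floor, power is about 0.54. Decline is lost faster than improvement.

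A common shortcut takes the share kept as 1 minus the share at the floor. That holds only for a vanishingly small effect. For a true +3 at 18% on the floor it gives 82%, against 90% above.

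**Power apart from any floor.** For one pairwise comparison, normal approximation: Φ(d·√(10/2) − 1.96). At d = 0.5 this is 0.20, at d = 0.8 it is 0.43, and at d = 1.0 it is 0.61. Power of 80% needs d = (1.96 + 0.84)·√(2/10) = 1.25, or 1.32 by the t distribution.

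**The case against.** A reader might infer that both measures sit at the end of their range, and that range alone makes the cognition question largely unanswerable. The documents do not support that.

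- **MoCA.** Nothing says where these participants score. Everything from 0 to 17 lies below the protocol's cut-off for normal, and the consent procedure provides for some participants who are oriented and can express understanding. A floor is foreseeable, not shown.
- **CDR.** A person at 1.5 or 2 has room both ways, and the cap at 3 does not hide the improvement being sought.
- **Timing.** On two of the three descriptions of its schedule, the CDR may not be repeated within the 10 weeks at all. That contradiction is better documented than any range problem.
- **Power.** Data Analysis admits that 10 per arm does not fully power the study, calls the behaviour-change results exploratory and says secondary outcomes could not be powered. A null result would be weak evidence without any floor.
- **Analysis.** The Statistical Analysis section names neither instrument, and the Table 3 it cites is not in the documents.

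Most of this stands, and it limits the claim to a risk of unknown size. It does not remove the point. The ANCOVA statement covers all secondary endpoints and both instruments are listed as secondary measures. That section also speaks of conclusions drawn from the ANCOVA, and attenuation at a floor adds to low power.

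**Conclusion.** The point holds as a risk of unknown size that the analysis does not check. A tool described as a screen for mild dysfunction is used in moderate to severe dementia, the CDR composite cannot register worsening at 3, and no analysis or reporting rule deals with scores at a limit.

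Under the assumptions stated, the MoCA loss is small if few are at the floor: at 18%, 90% of a 3-point gain and 76% of a 3-point decline are recorded. It is material if many are: at 54%, 62% and 38%. Actual scores decide which applies, and the documents give none. The small sample limits the cognition question in any case. What needs protecting is the reading of a null result, as regards both benefit and harm. The change is worth making because it is cheap; the point does not undermine the trial as a whole.

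**What to change.** 1. **Reconcile the documents first.** The CDR schedule in Secondary measures conflicts with the weeks 24 and 48 in the CDR paragraph and with the CDR's absence from Visits 9 and 10. The CDR entry criterion in Study Design conflicts with the one in the inclusion list and recruitment text.
2. **CDR.** Where it is measured after baseline, as Secondary measures plans, make the outcome the sum of the six area scores, adjusted for the baseline sum. Keep the composite for staging.
3. **MoCA.** Report by arm the number at the lowest score at baseline and at the end of the intervention. State that, when a material share is there, a null result is not evidence of no cognitive effect or of no cognitive harm.

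A rule that switches to an ordinal or censored model above a set share at the floor is not advised. It would depend on the data, and such models are fragile with 10 per arm.

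**Cost.** No new test or visit. The area scores already exist wherever the CDR is done. Because the Statistical Analysis section reports analyses already run, the change means a small reanalysis and some wording. The summed CDR score may still have a ceiling, since the documents give no range for the area scores.
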